10.3 Missing Data Handling

10.3.1 Missing Data Handling for Primary Efficacy Analysis

When the Flu-iiQ™ has missing values (unanswered questions), two different approaches to handle the missing data will be taken to evaluate the impact of missing data on the primary efficacy results.

- 1) Missing data will not be imputed and only recorded Flu-iiQ™ will be used for the analysis.

CONFIDENTIAL

21/62 page

Effective Date: 01-Aug-2018

Statistical Analysis Plan

- 2) On the other hand, missing data will be replaced by 0 or imputed using multiple imputation when at least one score on respiratory or constitutional symptoms in Domain 1 had been recorded.

Primary efficacy results from two different approaches will be compared to assess impact of missing imputation.

Prior to missing imputation, the number of missing values on a particular scale (respiratory or constitutional symptoms in Domain 1) will be considered in determining of way of imputation as follows:

2-1) If the number of missing items is less than half of the total number of items on a scale, missing values will be replaced by 0.

- a. Respiratory symptom scale: if one of three items is missing, the other two recorded items will be used assuming a missing item has 0 value.
- b. Constitutional symptom scale: if one of four items is missing, the other three recorded items will be used assuming a missing item has 0 value.

2-2) If the number of missing items is greater than or equal to half of the total number of items on a scale, multiple imputation will be conducted unless there is evidence that missing values would have 0 value.

2-2-1) Missing items are replaced by zero: when Flu-iiQ™ is not complete, then reason of not done recorded in eCRF will be manually reviewed. If subjects had indicated that they had ceased to complete the questionnaire because their symptom had disappeared or completed the questionnaire only on days when they experienced symptoms, missing items since then will be replaced by zero.

2-2-2) Multiple imputation: for any other cases, missing data will be imputed using multiple imputation method assuming Missing at Random (MAR). Several imputed datasets created by multiple imputations will be pooled.

Missing body temperature from diary will not be imputed, but when 3 subsequent time points have only missing value for middle of the time points and subject data indicates resolution of fever at the other two time points, then it can be considered that fever has resolved. The following examples should be used for reference:

- a. Example 1: Resolution of fever is considered to be maintained for 24 hours

Day 1 morning (10NOV16, 9:00 AM) Resolved
Day 1 evening (10NOV16, 9:00 PM) Missing
Day 2 morning (11NOV16, 9:00 AM) Resolved

- b. Example 2: Resolution of fever is not considered to be maintained for 24 hours

Day 1 morning (10NOV16, 9:00 AM) Resolved
Day 1 evening (10NOV16, 9:00 PM) Missing
Day 2 morning (11NOV16, 9:00 AM) Missing
Day 2 evening (11NOV16, 9:00 PM) Resolved

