10.1 Primary Efficacy Analysis

The primary efficacy endpoint analysis will assess the time from the administration of study drug to resolution of influenza symptoms and fever. The Flu-iiQ™ and body temperature recorded in diary including records as

Statistical Analysis Plan

a part of suspicious ADE assessment will be used for the analysis. The Flu-iiQ™ is a validated questionnaire with four domains. This includes the Domain 1; intensity of influenza symptoms, Domain 2; impact on activities, Domain 3; effects on feelings and Domain 4; concerns due to influenza. Subjects are offered four choices, ranging from the most positive response (e.g., none or not at all) to the most negative choice (e.g., severe or great difficulty). This analysis will be performed on the ITTI population.

The definitions of resolution of influenza symptoms and fever are described below.

Resolution of symptoms has occurred if all of the following influenza symptoms (as recorded on the Flu-iiQ™ of Domain 1) are mild in intensity or none for at least 24 hours. (4-point scale - 0: None, 1: Mild, 2: Moderate, 3: Severe).

- Respiratory symptoms (cough, sore throat, and nasal congestion)
- Constitutional symptoms (headache, feeling feverish, body aches and pains, and fatigue)

Resolution of fever is defined as:

- Body temperature (as recorded in the diary) of $<37.0^{\circ}\text{C}$ for at least 24 hours.

The start time for resolution of influenza symptom and fever is defined as the start time when symptoms and fever are resolved, whichever occurred latest.

The time (in days) from the administration of study drug to resolution of influenza symptoms and fever will be calculated as follows: [Start date/time of resolution of influenza symptoms and fever] – [Start date/time of study drug administration]. If time of completion of diary for Flu-iiQ™ and body temperature is missing then the time will be assumed to be 10:00 AM and 10:00 PM for Morning and Evening, respectively.

If the subject has received the drugs for symptom relief, the effective duration of the drugs for symptom relief should be considered in determining the start time for resolution of symptom and fever.

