The primary efficacy endpoint will be analyzed using a Wilcoxon rank-sum test to assess differences between treatment groups (CT-P27 45 mg/kg vs placebo, CT-P27 90 mg/kg vs placebo), if every subject is followed until resolution of influenza symptoms and fever. The Wilcoxon rank-sum test will be used to test for a statistical significant difference of time to resolution between placebo and CT-P27. The results of the analysis will be summarized using p-values. The significant level will be set to 5%. If p-value is lower than 5%, it is considered that there is a significant difference between placebo and CT-P27. For subjects who withdrew from the study before the symptoms have resolved or if the symptoms did not resolve until the data cut-off, data will be censored at the latest date/time recorded on the diary or start date/time of study drug administration when there are no recorded data on the diary after study drug administration. If there is any censoring, the primary efficacy endpoint will be analyzed using Log-rank test and Gehans Wilcoxon test, and the result will be presented by p-values from the two tests. Also the table will present count of censoring reasons and 25th percentile, median, 75th percentile of time from administration of study drug to resolution. Kaplan-Meier plots will be presented.

CONFIDENTIAL

Statistical Analysis Plan

If there are no censoring data, sensitivity analysis using tipping point analysis under Missing Not at Random (MNAR) will be also performed to explain varying cases about average unobserved outcomes dropouts on two treatment groups.

Sensitivity Analyses which alter resolution conditions of primary efficacy analysis will be performed on the ITTI population. Following two endpoints will be assessed as described for the primary efficacy endpoint.

- Time (in days) to resolution of influenza symptom (respiratory and constitutional symptoms)

In the analysis, fever is not considered and the definition of resolution of symptom is the same as those of primary efficacy analysis.

- Time (in days) to resolution of influenza symptom and fever

In the analysis, threshold of resolution of fever is changed to 37.8°C and the definition of resolution of symptom is the same as those of primary efficacy analysis.

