10.2 Secondary Efficacy Analyses

The secondary efficacy endpoints will be analyzed on the ITTI and ITT populations. For time-to-event analyses of secondary efficacy endpoints, records on diary for suspicious ADE assessment and unscheduled assessment of site body temperature will be used together with data from regular scheduled assessment.

- The following secondary efficacy endpoints will be analyzed using a Kaplan Meier model to assess differences between placebo and CT-P27. Missing time of completion of diary will be considered as described in the section for the primary efficacy endpoint:

- Time (in days) to resumption of normal activity as reported in Domain 2 of the Flu-iiQ™: [Start date/time of resumption of normal activity] – [Start date/time of study drug administration]

The resumption of normal activity has occurred if the degree of difficulty of all of the Domain 2 items are of no difficulty or some difficulty for at least 24 hours.

- Time (in days) to return to normal body temperature (<37.0°C) for at least 24 hours : [Start date/time of resolution of fever] – [Start date/time of study drug administration]

Data of body temperature recorded on the diary as well as the ones measured from the sites will be used to determine the return time to normal body temperature for at least 24 hours.

However, assessments which exceeds 24 hours measurement interval will be excluded because of lack of consecutiveness in determining the resolution.

If time of measurement of body temperature from site is missing, then the time will be imputed based on time of study drug administration such that missing body temperature assessment time on Day 3 will be imputed as: Infusion time + 48 hours. Missing times on other days will be imputed in the same manner.

- Time to resolution of individual symptoms for at least 24 hours as reported in Domain 1 of the Flu-iiQ™: [Start date/time of resolution of individual influenza symptoms] – [Start date/time of study drug administration]

The resolution of individual influenza symptoms will be determined as described for the primary efficacy endpoint.

- Severity of symptoms as recorded on the Domain 1 of the Flu-iiQ™
 - Impact of influenza symptoms consist of 4 scales of the items in Domain 1 (respiratory symptoms, constitutional symptoms, systemic symptoms, total symptoms)
 - Respiratory symptoms: cough, sore throat, and nasal congestion

Statistical Analysis Plan

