16. Sponsor-supplied or agreed in advance rapid influenza diagnostic test material will be used. And if there is available test result confirmed as influenza A prior to obtaining written informed consent and that result was from the influenza diagnostic test which is agreed with Sponsor in advance, that test result can be allowed. At screening, testing must be performed within 24 hours before study drug administration. Subjects with a negative test result by rapid diagnostic test, who have onset of symptoms within 48 hours (window of +12 hours is allowed) before study drug administration, can be rescreened only once.
17. The Investigator or designee will perform a symptom-directed physical examination (which should include, at a minimum, the examination of ear, nose, throat, sinuses, and lungs) and assessment for potential complications of influenza.
18. The subject will record the results of the Flu-iiQ™ in the diary.
 - Flu-iiQ™ will be recorded once by the subject at the screening visit and will be recorded twice a day (at approximately 12-hour intervals) from Day 1 to Day 8 (in the morning [between 6 and 10 AM, approximately] and in the evening [between 6 and 10 PM, approximately]).
19. Body temperature which a subject experiences in prior to screening will be collected and body temperature taken with any type of thermometer will be acceptable. However, from the screening period, Sponsor-supplied thermometer will be used.
 - Temperature will be measured by subject; It will be recorded twice a day (at approximately 12-hour intervals) from Day 1 to Day 8 (in the morning [between 6 and 10 AM, approximately] and in the evening [between 6 and 10 PM, approximately]).
 - Temperature will be measured by site personnel at site: at screening, Day 1 (prior to infusion), Day 2 (±4 hours), Day 3 (±4 hours), Day 5 (±4 hours) and Day 8 (±4 hours).
 - These will be used for assessment of endpoint.
20. Use of all medications, from 30 days prior to randomization and up until Day 110/EOS visit, will be recorded in the subject's eCRF.
21. AEs will be collected from the date the informed consent form is signed until Day 110/EOS visit.
22. EOS visit will be done at Day 110. But if a subject is early terminated from the study, EOS visit will be done to assess safety parameters at any time.

CONFIDENTIAL

37/62 page

Effective Date: 01-Aug-2018

Statistical Analysis Plan

Schedule of Assessments (Unscheduled Visits Subjects with Suspicious ADE)

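### A subject who stops the diary on recovery can have symptoms set to zero yet be censored for the primary endpoint, because trailing blank temperatures are not filled

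*SAP*

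**What the plan says.** SAP 10.1 takes the primary event at the "start time when symptoms and fever are resolved, whichever occurred latest". Each component must hold for at least 24 hours, and temperature is the diary temperature. Where there is no resolution, "data will be censored at the latest date/time recorded on the diary".

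SAP 10.3.1 sets out two approaches to missing questionnaire data. The first uses recorded answers only. The second fills gaps. Its rule 2-2-1 covers subjects who "ceased to complete the questionnaire because their symptom had disappeared", or who filled it in only on symptomatic days; for them "missing items since then will be replaced by zero".

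For temperature the section states: "Missing body temperature from diary will not be imputed". The one exception accepts a single missing reading between two resolved ones. Example 2 of that section refuses to bridge two consecutive missing readings.

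Site staff also measure temperature at screening and on Days 1, 2, 3, 5 and 8. For the secondary fever endpoint, SAP 10.2 says "Data of body temperature recorded on the diary as well as the ones measured from the sites will be used", and drops assessments more than 24 hours apart. Footnote 19 of the schedule (SAP 14.1) lists the diary and site readings together and adds: "These will be used for assessment of endpoint".

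**The concern.** Rule 2-2-1 shows that the authors expected some subjects to stop the questionnaire because they were well, and did not want this to count as non-resolution. The rule repairs only one half of a composite event. Temperature is entered in the same diary (Protocol 6.1.1). If it stops at the same time, the fever half stays open and the subject leaves the risk set because of recovery.

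Censoring of this kind depends on the outcome. It makes Kaplan-Meier times to resolution too long, removes events and costs power. Arm-level times matter here because SAP 1.1 says that the data will be used to establish an effect size and to select doses for later studies.

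**Working it through.** **The plan's own figures.** SAP 5.2 gives 63 per CT-P27 arm and 38 on placebo, a 1.8-day reduction, SD 3 days, two-sided 5%, and 80% power by Wilcoxon.
- With the normal-theory Wilcoxon efficiency 3/π, the effective sizes are 38 × 0.955 = 36.3 and 63 × 0.955 = 60.2.
- z = 1.8 / (3 × √(1/36.3 + 1/60.2)) = 2.855. Power = Φ(2.855 − 1.960) = 81.4%, which agrees with 80%.
- 164 / 0.90 = 182.2, rounded up to 183, as stated.

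Neither figure depends on the rule discussed here, so there is no corrected sample size.

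**Applying the rules.** Take infusion at 12:00 on Day 1 and 12-hourly diary slots at 8, 20, 32, ... hours. The first entry below 37.0°C with all symptoms at most mild is at 92 h. The subject then stops the whole diary because symptoms have gone.

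| Last diary entry | Symptoms, approach 2 | Fever | Result |
|---|---|---|---|
| 92 h | resolved at 92 h | not resolved | censored at 92 h |
| 104 h | resolved at 92 h | not resolved | censored at 104 h |
| 116 h or later | resolved at 92 h | resolved at 92 h | event at 92 h |

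In the first two rows the single-gap exception fails because no later diary reading exists. Under approach 1 these two subjects have neither component resolved and are censored as well. The planned comparison of the two approaches therefore cannot show the problem.

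**Size.** The documents give neither the share affected, q, nor the placebo mean, so both are assumed.
- Times are gamma with SD 3, placebo mean 5 days, active mean 5 − 1.8 = 3.2 days.
- A share q of those resolving before 6.4 days is censored 12 hours after resolution.
- Subjects unresolved at 6.4 days are censored at 7.4 days.
- The test is log-rank, 63 against 38, two-sided 5%. Power is a range over repeated runs.

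| q, both arms | Placebo median (days) | Active median (days) | Difference (days) | Power |
|---|---|---|---|---|
| 0 | 4.4 | 2.3 | 2.1 | 83% |
| 5% | 4.55 | 2.46 | 2.1 | 79-80% |
| 10% | 4.7 | 2.6 | 2.1 | 77-78% |
| 20% | 5.05 | 2.95 | 2.1 | 71-73% |

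A variant with placebo mean 5.5 days and times on a 12-hour grid gives power of 79%, 79%, 76% and 72% for the same four values of q. At q = 10% in both arms and no true effect, its type I error stays at 5%.

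**What site readings could repair.** The Day 5 site reading is due at 96 h and the Day 8 reading at 168 h (each ±4 h).
- First normal entry at 68 h (Day 4 morning), last entry at 80 h: the gap to the site reading is 96 − 80 = 16 h, and the run is 96 − 68 = 28 h. If the site reading is below 37.0°C, this is an event at 68 h.
- Last entry at 104 h, as in the first table: the gap to Day 8 is 168 − 104 = 64 h. A 24-hour limit leaves this subject censored.

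**The case against.** Four objections carry weight.

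**The link between symptoms and temperature is inferred.** A reader might take every subject under rule 2-2-1 to be censored. The documents do not support that. Questionnaire and temperature are separate diary entries, and a subject may drop one and keep the other. A subject already below 37.0°C for 24 hours when the diary stops is an event. If half of the stoppers had a short fever run (an assumption), 10% stopping would mean q = 5%. The table is therefore stated for subjects actually affected, not for all stoppers. Staff also review diaries and repeat instructions at visits (Protocol 6.1.1).

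**A planned analysis partly covers this.** SAP 10.1 includes a sensitivity analysis without fever. If rule 2-2-1 carries over, the affected subject is an event there. The table list (SAP 14.7) shows one table for it and no separate imputed version, so this is not certain. A second analysis at 37.8°C would leave fewer short runs. Neither repairs the main analysis.

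**Absence of symptoms is not a temperature.** Treating the two components differently is defensible. This argues against imputing temperature, but not against using readings that were actually taken.

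**The censoring is itself an inference.** The sentence in SAP 10.1 names only unresolved symptoms. Censoring is the natural reading for a composite event, but the text does not say so.

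A reader might also infer a biased treatment comparison, or set the arm-level shift against the 1.8-day effect. With equal shares the shift appears in both arms and largely cancels. Unequal shares would do harm: in the 5.5-day variant, 5% against 20% with no true effect gives a type I error of about 12%. Nothing in the documents indicates unequal shares.

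**Conclusion.** The gap is real but narrow. It needs three things together: the diary stops because of recovery, temperature recording stops with it, and readings below 37.0°C span less than 24 hours at that point. For such a subject the imputed analysis accepts symptom resolution, leaves fever unresolved and, on the natural reading, censors at recovery or about 12 hours later.

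The frequency is unknown. At 5% to 20% affected equally, arm medians are about 0.1 to 0.6 day late and power is about 3 to 12 points lower, under the assumed gamma times. The contrast between arms is nearly unchanged. To say that blank temperatures are never filled would go too far, since single gaps are bridged; the gap concerns trailing blanks only. This is an improvement worth making, not a flaw that undermines the trial.

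**What to change.** 1. In SAP 10.1 and 10.3.1, let the site temperatures of Days 2, 3, 5 and 8 count towards the primary 24-hour fever run, in line with footnote 19 and the secondary fever endpoint. Apply the same limit of at most 24 hours between consecutive readings, and the same allowance for the effective duration of symptom-relief drugs.
2. Where the gap is longer, keep the subject censored in the main analysis. This respects Example 2 of SAP 10.3.1 and the 24-hour limit in SAP 10.2. Add a sensitivity analysis for subjects who meet rule 2-2-1 and whose last diary temperature and next site temperature are both below 37.0°C, counting fever as resolved from the start of that run.
3. State in SAP 10.1 how a subject with symptoms resolved but fever unconfirmed is censored.
4. Report the number of affected subjects per arm. If it is small, the count settles the matter.

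The cost is SAP wording and a little programming on data already collected. The downside is that the primary fever component then mixes diary and site readings. That departs from the diary-only wording and should be listed in SAP section 13. Long-gap subjects remain censored in the main analysis, so the repair is partial.

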10.3.2 Missing Data Handling for Secondary Efficacy Analyses

10.3.2.1 Time to Resumption of Normal Activity as Reported in Domain 2 of the Flu-iiQ™

If the number of missing items on Domain 2 is less than half of the total number of items on the domain, missing values will be replaced by 0 (same rule as 2-1 in section 10.3.1). Otherwise, it cannot be considered

Statistical Analysis Plan

that normal activity is resumed.

10.3.2.2 Time to Return to Normal Body Temperature (<37.0°C) for at Least 24 hours

Missing body temperature from diary or sites will not be imputed. However when there are missing values between two time-points with interval 24 hours at which normal body temperature are reported, it can be considered that fever is resolved for 24 hours.

10.3.2.3 Time to Resolution of Individual Symptoms for at Least 24 hours as Recorded on the Flu-iiQ™

The same rule for missing body temperature described in section 10.3.1 will be applied.

10.3.2.4 Severity of Symptoms as Recorded on the Flu-iiQ™

If the number of missing items on each scale of Domain 1 is less than half of the total number of items on the scale, only the recorded items are used for the analysis. Otherwise, data of that visit will be excluded from the analysis.

10.3.2.5 Quality of Life Measures as Reported in Domain 3 and Domain 4 of the Flu-iiQ™

The same rule as described in section 10.3.2.4 will be applied.

11. Exploratory Analysis

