- Constitutional symptoms: headache, feeling feverish, body aches and pains, and fatigue
- Systemic symptoms: headache, feeling feverish, body aches and pains, fatigue, neck pain, interrupted sleep, and loss of appetite
- Total score: all items in Domain 1

Descriptive statistics of actual value and change from baseline for average score in each scale will be presented by treatment group at each visit.

If there are missing values in items in Domain 1, missing data will be handled according to section 10.3.

- Descriptive analysis for AUC of average symptom score from date of baseline assessment to last measurable value of subjects who have at least one post-baseline result.

If there are missing values in average symptom scores between observed ones, the missing values are assumed to fall linearly between observed values.

- Mean daily symptom score on the Domain 1 of the Flu-iiQ™

Average of total symptom score for each time point will be plotted with the SD of mean score.

- Incidence of symptoms on the Domain 1 with Grade 2 or Higher

The proportion of subjects who developed any of the 7 individual influenza symptoms (cough, sore throat, nasal congestion, headache, feeling feverish, body aches and pains, and fatigue from Flu-iiQ™ Domain 1) with moderately or severe in intensity (Grade 2 or higher) will be calculated from baseline to Day 8. Most severe score will be counted per each day. Subjects with incomplete data and no recorded symptoms will not be counted (i.e. did not experience symptoms Grade 2 or higher).

All item scores of Flu-iiQ™ will be listed by each domain and time point. Additional listing for Flu-iiQ™ will be provided including average score of Domain 1 (respiratory, constitutional, systemic, total symptom score), Domain 3, Domain 4 and AUC of Domain 1.

- Viral shedding in nasopharyngeal swab samples

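### The symptom-severity means drop diary entries left blank because symptoms had gone, while the imputation approach to the primary analysis scores such entries as 0

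*SAP*

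**What the plan says.** **Severity endpoint.** SAP 10.2 plans, for the respiratory, constitutional, systemic and total scales: "Descriptive statistics of actual value and change from baseline for average score in each scale will be presented by treatment group at each visit". It adds a plot of the mean total score, a symptom AUC and the incidence of Grade 2 or higher symptoms. The missing-item rule is in SAP 10.3.2.4. When the number missing is "less than half of the total number of items on the scale, only the recorded items are used for the analysis"; with half or more missing, "Otherwise, data of that visit will be excluded from the analysis".

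**Primary endpoint.** SAP 10.3.1 sets out two approaches and compares their results. In the first, "Missing data will not be imputed and only recorded Flu-iiQ™ will be used for the analysis". The second imputes, and its rule 2-2-1 calls for manual review of the reason a questionnaire was not completed. Where that reason is that the subject stopped once free of symptoms, or filled in the diary on symptomatic days alone, "missing items since then will be replaced by zero".

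**Individual symptoms.** SAP 10.3.2.3 says only: "The same rule for missing body temperature described in section 10.3.1 will be applied". SAP 10.2, however, says that resolution of individual symptoms is determined as for the primary endpoint.

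Neither SAP section 13 nor protocol 8.6.1 carries the zero rule over to severity.

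**The concern.** The SAP foresees subjects who stop the diary because they are well, and it reviews the recorded reason. Where that reason is recovery, the entry is not an unknown value: by the SAP's own reading the score is 0. Under 10.3.2.4 the entry leaves the severity summaries, so exclusion depends on the outcome being summarised. The visit mean then describes those still recording rather than the arm, and the arms can lose different shares of records if they recover at different speeds. Severity is a named secondary efficacy endpoint in a study meant to inform dose selection.

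**Working it through.** The documents state no figure on this point, so there is none to reproduce. The check has three steps.

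**1. Does a blank entry fall under the exclusion?** The scales have 3 (respiratory), 4 (constitutional), 7 (systemic) and, counting the respiratory and systemic items that SAP 10.2 lists, 3 + 7 = 10 items (total). A blank entry has 3/3, 4/4, 7/7 and 10/10 missing. Each is at least half, so the entry leaves all four averages and the mean plot. Rule 2-2-1 would set the respiratory and constitutional items of that entry to 0.

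**2. Effect on one arm's mean.** Let m be the mean among recorders and r the share of records dropped because symptoms had gone. The recorded-only mean is m and the zero-filled mean is m(1-r), so the overstatement is 1/(1-r):

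| r (assumed) | Factor |
|---|---|
| 10% | 1/0.90 = 1.11 |
| 20% | 1/0.80 = 1.25 |
| 40% | 1/0.60 = 1.67 |
| 60% | 1/0.40 = 2.5 |

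**3. Effect on the difference between arms.** From the SAP's sample-size section: SD 3 days, effect 1.8 days. Assumed: gamma resolution times; placebo mean 5 or 6 days; average score falling from 1.8 to 0.7 at resolution, then to 0 over 1, 2 or 3 days; a share q of symptom-free subjects stops recording, equal in both arms. Then r = q × (share of the arm at score 0). This was simulated with 400,000 subjects per arm, read at 3.5, 4.5, 5.5, 6.5 and 7.2 days.

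| q | CT-P27 mean inflated by (4.5-7.2 days) | Change in size of difference, points (3.5-7.2 days) | Same, relative |
|---|---|---|---|
| 20% | 3% to 21% | -0.027 to +0.014 | -8% to +13% |
| 30% | 5% to 35% | -0.043 to +0.021 | -12% to +20% |

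Two cases (placebo mean 5 days, 1-day tail) show the change of sign:

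- At 3.5 days with q = 20%, r is 10.5% on CT-P27 and 4.1% on placebo. CT-P27: 0.4217/(1-0.1055) = 0.471. Placebo: 0.7767/(1-0.0409) = 0.810. The difference shrinks from 0.355 to 0.338.
- At 7.2 days with q = 30%, r is 25.9% and 21.5%. CT-P27: 0.1080/(1-0.2587) = 0.146. Placebo: 0.2157/(1-0.2151) = 0.275. The difference grows from 0.108 to 0.129. The 35% inflation is this move from 0.108 to 0.146.

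Larger distortions need more extreme inputs. If recorders in both arms averaged 1.0 and 20% versus 10% of records were dropped, the recorded-only difference would be 0 and the zero-filled one 0.8 - 0.9 = -0.1. But with q = 30%, r = 20% means 0.20/0.30 = 67% of the arm is symptom-free. Most of those still recording would then score 0, and a recorder mean of 1.0 is hard to sustain.

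**Outputs that escape.** The AUC ends at the last measurable value; adding zeros afterwards changes only the final segment down to 0. The Grade 2+ incidence already reads incomplete data with no recorded symptoms as no Grade 2+ symptom.

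**The case against.** The other side has several good points.

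- A reader might infer that the primary analysis as a whole scores these entries as 0. It does not: approach 1 leaves them missing. Approach 2 also requires at least one recorded respiratory or constitutional score, without saying whether at that entry or at any time. On the first reading a wholly blank entry would not qualify. This stands and limits the point to approach 2.
- A reader might infer a systematic dilution of the treatment effect, with the ratio of means pulled towards 1. The SAP plans no ratio of means, and the pull depends on assuming a real effect and equal stopping behaviour by arm. On the planned scale the bias changes sign.
- A reader might infer that a subject resolved in the imputed primary analysis would be censored for individual symptoms under 10.3.2.3. That section does carry over only a rule needing resolved readings on both sides of a single gap, but SAP 10.2 refers back to the primary definition. The texts need reconciling; they do not establish the censoring.
- The stopping share is assumed. Protocol 6.1.1 has staff review diaries and encourage completion, so q may be low. The SAP reports n with each summary and lists all item scores, so lost records would be visible, though the reason would not appear in the table.
- SAP 10.2 sends missing Domain 1 items to section 10.3 in general, so a programmer could argue that 2-2-1 applies. But 10.3.1 is headed for the primary analysis and 10.3.2.4 is specific to severity.

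None of this supplies the missing exception in 10.3.2.4.

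**Conclusion.** The point holds in a limited form. Followed as written, 10.3.2.4 removes entries that the SAP elsewhere treats as known zeros, and the visit means, change-from-baseline tables and mean plot overstate severity by 1/(1-r). That factor is exact given r, but r is not in the documents. Under the assumed model with 20-30% of symptom-free subjects stopping, the between-arm difference moves by no more than 0.043 points, tending to be understated early and overstated late. The documents do not support calling this a threat to the trial's conclusions: severity is secondary and summarised without a test, and the primary test does not use this rule. It is an inconsistency worth removing because removal is cheap and the exclusion depends on outcome.

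**What to change.** - **10.3.2.4:** apply the 2-2-1 reason review first. Where the reason is that symptoms had gone, or that the subject recorded only on symptomatic days, set the respiratory and constitutional items to 0 from then on. State whether this extends to neck pain, interrupted sleep and loss of appetite, which 2-2-1 does not cover but the systemic and total scales include. Exclude only the remaining visits with half or more items missing.
- **Tables:** show the number of zero-filled records per visit and arm.
- **10.3.1:** say whether the recorded score that approach 2 requires must be at that entry or may be at any time.
- **10.3.2.3:** reconcile with the statement in 10.2 on individual symptoms.
- **10.3.2.5:** say whether quality-of-life Domains 3 and 4 keep the existing exclusion. They borrow the 10.3.2.4 rule, and absence of symptoms does not by itself make those scores 0.

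The cost is a few sentences and one added table row, with no new data collection. The reason review is planned for the primary analysis on ITTI; severity is also summarised on ITT, so the review must be extended to ITT subjects outside ITTI.
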